#### 4.4.2 Management and grading of infusion reactions

The BI 836845 infusion should always be administered under close supervision of a medically qualified staff member with immediate availability of appropriate resuscitation facilities.

Infusion reactions may occur during infusion with BI 836845 and include pyrexia, chills, rigors, dyspnoea, urticaria, bronchospasm, hypotension and hypertension. **A one hour observation period is recommended following each infusion.** If there is no infusion reaction during the first treatment course, the observation period following BI 836845

Proprietary confidential information.

© 2016 Boehringer Ingelheim International GmbH or one or more of its affiliated companies. All rights reserved.

This document may not - in full or in part - be passed on, reproduced, published or otherwise used without prior written permission.

infusion may be adjusted at the discretion of the investigators. Mild to moderate infusion reactions may be managed with a slower infusion rate and prophylactic antihistamines for subsequent dosing. Severe reactions require immediate and permanent discontinuation of infusion. The hypersensitivity reactions will be graded according to the National Cancer Institute (NCI) Common Terminology Criteria for Adverse Events (CTCAE) version 4.03 ([R10-4848](#)).

Table 4.4.2: 1 Infusion reaction management

Infusion Reaction Grade	Management
CTCAE Grade 1 or 2	In the event of a CTCAE grade 1 infusion reaction, the infusion rate should be reduced by 50%. Grade 2 infusion reaction may require symptomatic treatment (e.g., antihistamines, NSAIDs, steroids, narcotics, IV fluids) with infusion interruption. Once the event has resolved, the infusion may be restarted at the reduced rate.
CTCAE Grade 3	For patients experiencing CTCAE grade 3 infusion reaction, infusion should be interrupted immediately and patients should receive aggressive symptomatic treatment. Only after all the symptoms have disappeared, the infusion may be re-started if it is within 3 hours since the infusion start. The infusion rate should be reduced by half if it is restarted.
CTCAE Grade 4	Patients experiencing CTCAE grade 4 such as anaphylaxis during an infusion should have infusion immediately stopped and receive appropriate treatment including use of resuscitation medications and equipment that must be available. Such patients should NOT receive any further BI 836845 treatment.

The infusion duration may be extended to over one hour and up to a maximum of three hours, see [Section 4.1.4](#).

The infusion reactions should be treated symptomatically as judged clinically relevant by the investigator. For symptomatic treatment of infusion reactions: hydrocortisone, antihistamines such as chlorphenamine accompanied by an antipyretic/analgesic and/or a bronchodilator is recommended.

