#### 4.1.1 Identity of BI investigational product and comparator products

##### 4.1.1.1 BI 836845 (investigational product)

Substance:	BI 836845 human monoclonal antibody
Pharmaceutical form:	Liquid formulation
Source:	Boehringer Ingelheim Pharma GmbH & Co. KG
Unit strength:	10 mg/ml of BI 836845 supplied in 20 ml vials (200 mg/vial)
Weekly dose	1000 mg, 750 mg (starting dose)
Posology:	Once weekly administrated through one hour intravenous infusion. Infusion duration may be extended to over one hour and up to a maximum of three hours in cases of grade $\geq 2$ infusion reactions
Route of administration:	Intravenous infusion. Appropriate dose of BI 836845 will be diluted in isotonic sodium chloride solution (0.9%)
Duration of use:	Continuous weekly dosing (days 1, 8, 15 and 22 in a 28-day course) in the absence of disease progression, intolerable AEs or other reason necessitating withdrawal

Detailed preparation and handling of BI 836845, including information on infusion equipment and infusion procedure, will be described in ISF.

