##### 4.1.4.1.1 BI 836845

Patients will start treatment with their assigned dose tier (see [Section 4.1.3](#)) or RP2D of BI 836845 from course 1 day 1. BI 836845 will be administered at the investigator site intravenously over one hour with a constant infusion rate on the treatment day as specified in the [Flow Chart](#). If scheduled infusion of BI 836845 is not performed within the time window, this treatment will be skipped and will not be made up. Subsequent visits should follow the original visit date schedule. Mannitol is used in the formulation of BI 836845, so an infusion duration of less than one hour must be avoided. The infusion time may be extended to over one hour and up to a maximum of three hours in cases of CTCAE grade  $\geq 2$  infusion reactions (see [Section 4.4.2](#) for grading and management of infusion reactions). Further information on infusion equipment and procedure is described in the ISF. In case of a delay or an interruption of infusion, the reason and the exact time of deviation must be recorded in the eCRF. The accuracy of this information is crucial for the proper evaluation and appraisal of the pharmacokinetics and other data.

**At days of PK sampling during the Phase I and II part, everolimus and exemestane should be administrated within 5 minutes after start of BI 836845 infusion.**

Detailed information of dispensation, preparation, and handling of BI 836845 will be described in ISF.

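### Protocol Section 4.4.2 contradicts its own table on resuming an infusion after a grade 3 infusion reaction, and the three-hour maximum duration does not say whether pauses count

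*Protocol*

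**What the plan says.** The running text of Protocol Section 4.4.2 sorts infusion reactions into two classes. For the lower class: "Mild to moderate infusion reactions may be managed with a slower infusion rate and prophylactic antihistamines for subsequent dosing". For the upper class: "Severe reactions require immediate and permanent discontinuation of infusion". It then says that reactions are graded by CTCAE version 4.03.

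Table 4.4.2: 1 works by grade. Grades 1 and 2 share a row and are managed by rate reduction, with interruption and symptomatic treatment for grade 2. At grade 3 the infusion is interrupted at once and treated aggressively, but: "Only after all the symptoms have disappeared, the infusion may be re-started if it is within 3 hours since the infusion start". The rate is then halved. At grade 4 the infusion is stopped, and: "Such patients should NOT receive any further BI 836845 treatment".

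A separate limit on total duration appears in three places:
- Section 4.1.1.1: "Infusion duration may be extended to over one hour and up to a maximum of three hours in cases of grade" 2 or higher reactions.
- Section 4.1.4.1.1: "The infusion time may be extended to over one hour and up to a maximum of three hours in cases of CTCAE grade" 2 or higher reactions.
- Section 4.4.2, after the table: "The infusion duration may be extended to over one hour and up to a maximum of three hours".

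In the SAP, code C3 of Table 6.2: 1 flags a xentuzumab infusion shorter than 50 or longer than 200 minutes. It asks that interruptions be allowed for when the duration is calculated.

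**The concern.** This is an instruction that staff must act on at the bedside. If severe includes grade 3, a site following the text may not resume the infusion, while a site following the table may. Both could claim to follow the protocol.

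The duration limit raises a smaller problem. The table allows a restart late in the three-hour window, but a late restart may not be able to finish inside the three-hour maximum. Whether it can depends on whether the pause counts, which is not stated. The same gap carries into the SAP, where C3 is marked as automatically derived, so a programmer has to choose one way of counting.

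**Working it through.** **Step 1: text and table side by side.**

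| CTCAE grade | Text of 4.4.2 (if severe means grade 3 and above) | Table 4.4.2: 1 |
|---|---|---|
| 1 or 2 | Slower rate; antihistamines for later doses | Slower rate; interruption and symptomatic treatment for grade 2 |
| 3 | Infusion ended for good | Interrupted; restart at half rate optional |
| 4 | Infusion ended for good | Stopped; no further drug |

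The rows agree on direction except at grade 3. Restart is optional in the table, so a site that never restarts satisfies both. The conflict is that one instruction forbids what the other allows.

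**Step 2: does another section settle it?** None found does.
- Section 4.1.4.3 sends the reader back to Section 4.4.
- The catch-all grade 3 or higher line of the DLT definition (Section 5.2.6) leaves out infusion reactions.
- Sections 2.3 and 4.4 let local or institutional guidance be used, but do not say which instruction applies where none is substituted.

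**Step 3: restart window against maximum duration.** Inputs: a 60-minute constant-rate infusion (Section 4.1.4.1.1); half rate on restart, and restart allowed up to minute 180 from the start (Table 4.4.2: 1); a maximum of 180 minutes. Assumptions: the reaction is at minute t, restart is at elapsed minute r, and the rate is halved once. The values of t and r are illustrations.

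- Dose left at the reaction: 60 − t full-rate minutes, taking 2(60 − t) minutes at half rate.
- Infusing time: t + 2(60 − t) = 120 − t.
- Elapsed time at the end: r + 2(60 − t).
- To finish by minute 180 elapsed: r ≤ 180 − 2(60 − t) = 60 + 2t.

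| t | Latest restart to finish by 180 elapsed | Elapsed if restarted at 180 | Infusing time |
|---|---|---|---|
| 15 | 60 + 30 = 90 | 180 + 90 = 270 | 105 |
| 30 | 60 + 60 = 120 | 180 + 60 = 240 | 90 |
| 45 | 60 + 90 = 150 | 180 + 30 = 210 | 75 |

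If pauses count, a restart the table permits can exceed the maximum. If they do not, one halving gives at most 120 minutes and the maximum is met.

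With two halvings the maximum can be exceeded even without counting pauses. Take a grade 1 reaction at minute 10 (rate halved) and a grade 3 reaction at minute 20 (halved again on restart). By minute 20, 10 + 5 = 15 full-rate minutes have been given. The remaining 45 take 180 minutes at quarter rate, so infusing time is 20 + 180 = 200 minutes.

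**Step 4: SAP C3.** Each of the three restarts at minute 180 exceeds 200 minutes elapsed and is well under 200 minutes infusing. Each is therefore flagged or not according to an unstated choice.

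**Step 5: what changes at the visit.** With t = 15, 15/60 = 25% of the dose has been given. The text leaves it there. The table allows anything from 25% (no restart) to 100% (completed).

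**Step 6: frequency.** Section 2.3 reports no infusion reaction in 81 monotherapy patients. The one-sided 95% upper bound is 1 − 0.05^(1/81) = 3.6%. That covers reactions of any grade on monotherapy. It does not isolate grade 3 and need not carry over to the combination.

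**The case against.** The strongest defence is that severe means grade 4 only, which would remove the conflict. The wording gives this some support: the table says grade 3 infusions are interrupted but grade 4 infusions are stopped, and a permanent stop sits closer to the grade 4 row. The text also goes straight from naming CTCAE to the graded table, which a site would naturally use. Against this, the text has only two classes. If severe were grade 4 only, grade 3 would be either mild to moderate, although the table separates it from grades 1 and 2, or not covered at all. What stands is that reading severe as including grade 3 is an inference, though the more natural one. A reader might infer that the protocol expressly bars restart at grade 3; it does not say so in terms.

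A second defence is that Section 4.4 is a recommendation that institutional guidelines may replace. Some variation between sites is therefore allowed by design, and reconciling the wording will not remove it. The protocol's own default should still be single.

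A third is that C3 is clear enough: a plain start-to-end duration already contains the pauses, so asking for interruptions to be allowed for adds something only if they are subtracted. That is a reasonable reading, but the SAP does not state it.

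A reader might also infer that the three-hour restart limit has no defined starting point. The documents do not support that: the grade 3 row counts from the infusion start. Only the separate maximum duration is silent, and only on pauses.

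**Conclusion.** The text and table of Section 4.4.2 need to be reconciled for grade 3 reactions. The conflict rests on reading severe as grade 3 and above, which is the most natural reading but not a stated one. The counting of pauses is a genuine but minor second gap.

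The size is small. It concerns how one uncommon event is handled, the dose given at that visit, and C3 reporting. Table 6.2: 1 is a working list of potentially important violations, and C3 excludes no patient. PFS, sample size and analysis sets are unaffected.

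A reader might go further and put a figure on lost dose intensity over a course of treatment. The documents do not support one: the text does not say whether the permanent stop applies to that infusion or to the drug, and the grade 3 rate is not given. The timing figures assume a 60-minute constant-rate infusion and, except where stated, a single halving.

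The SAP says xentuzumab was stopped on 28 October 2016 and follows protocol amendment 3, which is not among the documents. Whether this wording was later changed is unknown.

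**What to change.** The sponsor's medical team should reconcile the text and table of Section 4.4.2 with Sections 4.1.1.1 and 4.1.4.1.1, so that each CTCAE grade has one instruction on stopping, resuming and maximum duration. The word severe should be replaced by a CTCAE grade. The protocol should state whether pauses count toward the three-hour maximum, and SAP code C3 should use the same definition. No view is given on which clinical rule is right.

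The cost is protocol wording, a notice to sites and one line in C3. No new data should be needed, since Section 4.1.4.1.1 already requires: "In case of a delay or an interruption of infusion, the reason and the exact time of deviation must be recorded in the eCRF". With xentuzumab stopped, mainly the C3 wording could still be applied in this trial. The protocol wording matters for any later trial that reuses the section.

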#### 4.4.3 Management of hyperglycemia and hyperlipidemia

In case of hyperglycaemia and hyperlipidemia, treatment should follow institutional standard, prescribing information for everolimus and/or guideline ([R13-1975](#)). Monitoring of fasting serum glucose is recommended prior to the start of everolimus therapy and periodically thereafter. Optimal glycemic control should be achieved before starting trial therapy. After commencing the study medication, in patients with diabetes, fingerstick glucose values should be monitored daily. If fasting glucose values above 200 mg/dL occur, the investigator should evaluate the need to intensify antihyperglycemic therapy potentially in

Proprietary confidential information.

© 2016 Boehringer Ingelheim International GmbH or one or more of its affiliated companies. All rights reserved.

This document may not - in full or in part - be passed on, reproduced, published or otherwise used without prior written permission.

collaboration with the treating physician responsible for the treatment of the diabetic condition or a specialist. For hyperglycemia occurs to patients without history of diabetes or hyperglycemia, oral anti-diabetics, such as metformin 1 g to 2.5 g/d with less hypoglycemic risk, may be started if necessary.

In case of grade 3 or higher hyperglycemic event, the patient should have immediate access to consultation with an endocrinologist or specialist. When the study drug is discontinued, the need for further antidiabetic treatment has to be evaluated depending on the blood glucose levels of the patient.

#### **4.4.4 Management of non-infectious pneumonitis**

Non-infectious pneumonitis is a class effect of rapamycin derivatives. Fatal cases of non-infectious pneumonitis (including interstitial lung disease) have occurred. The investigator should monitor patients for clinical symptoms or radiological changes. For dose reduction, interruption or discontinuation of everolimus in the management of non-infectious pneumonitis, refer to everolimus SPC or prescribing information of respective country.

#### **4.4.5 Management of viral hepatitis**

Everolimus has immunosuppressive properties and may predispose patients to viral infection including reactivation of hepatitis virus. Please follow the current label of everolimus and local guidance should treatment for viral hepatitis is needed.

Prior to study treatment, patients must be screened for hepatitis risk factors and any past and current illnesses of hepatitis B and hepatitis C. Refer to [Flow Chart](#) for lab screening of Hepatitis B and C. Patients with baseline positive HBV-DNA or positive HbsAg, positive HCV-RNA or positive anti-HCV Ab are not eligible for the study.

#### **4.4.6 Management of infection (related to everolimus)**

Everolimus has immunosuppressive properties and may predispose patients to bacterial, fungal, viral or protozoan infections, including infections with opportunistic pathogens. Opportunistic infections such as pneumocystis jirovecii (carinii) pneumonia (PJP, PCP) have been reported in patients who received everolimus and should be ruled out in the differential diagnosis of non-infectious pneumonitis. Prophylaxis for PJP/PCP should be considered when concomitant use of corticosteroids (e.g. for treatment of non-infectious pneumonitis) or other immunosuppressive agents are required.

Please follow the most current everolimus SPC or local prescribing information for updated recommendations of management.

Proprietary confidential information.

© 2016 Boehringer Ingelheim International GmbH or one or more of its affiliated companies. All rights reserved.

This document may not - in full or in part - be passed on, reproduced, published or otherwise used without prior written permission.

## 5. VARIABLES AND THEIR ASSESSMENT

### 5.1 EFFICACY - CLINICAL PHARMACOLOGY

#### 5.1.1 Endpoints of efficacy

##### 5.1.1.1 Primary endpoint

**Phase II part:** Progression-free survival (PFS).

PFS is defined as the duration of time from the date of randomization until the date of the first objective tumor progression according to RECIST 1.1 or death due to any cause, whichever occurs earlier. If a patient has not had an event, PFS will be censored at the date of last adequate tumor assessment.

##### 5.1.1.2 Secondary endpoints

**Phase II part:**

1. Time to progression (TTP), defined as the duration of time from the date of randomization until the date of the first objective tumor progression according to RECIST 1.1.
2. Objective response (OR), defined as best overall response of complete response (CR) or partial response (PR) (CR + PR), where best overall response is determined according to RECIST 1.1 from date of randomisation until the earliest of disease progression, death or last evaluable tumor assessment before start of subsequent anti-cancer therapy.
3. Time to objective response, defined as the time from randomisation until first documented CR or PR.
4. Duration of objective response, defined as the time from first documented CR or PR until the earliest of disease progression or death among patients with OR.
5. Disease control (DC), defined as best overall response of complete response (CR) or partial response (PR), or stable disease (SD)  $\geq 24$  weeks, or Non-CR/Non-PD for  $\geq 24$  weeks, where best overall response is defined according to RECIST 1.1 from date of randomisation until the earliest of disease progression, death or last evaluable tumor assessment before start of subsequent anti-cancer therapy.
6. Duration of disease control, defined as the time from randomisation until the earliest of disease progression or death, among patients with disease control.

Proprietary confidential information.

© 2016 Boehringer Ingelheim International GmbH or one or more of its affiliated companies. All rights reserved.

This document may not - in full or in part - be passed on, reproduced, published or otherwise used without prior written permission.

## 5.1.2 Assessment of efficacy

### 5.1.2.1 Tumor response

Response and progression will be evaluated in this study using Response Evaluation Criteria in Solid Tumors (RECIST) guideline (version 1.1) ([R09-0262](#)). Tumor response will be assessed by local investigator's review.

For the Phase II part of the study, image acquisition will be performed as described in the Imaging Guideline (which will be filed in the ISF). Images will be collected and stored at a central facility assigned by the sponsor. The sponsor retains the option to perform an independent blinded central review of the study images at a later time.

See [APPENDIX 10.4](#), RECIST 1.1 (R09-0262) for details on lesion measurements and response assessment.

Every effort should be made to objectively evaluate tumor response for all patients who enter into the trial, including those who discontinue prematurely.

RECIST 1.1 will be followed in this study for tumor assessment. Tumor assessments should include scans of the chest, abdomen and pelvis. If clinically indicated, imaging of any other known or suspected sites of disease (e.g. breast, neck, brain etc) should be performed using an appropriate method (CT/MRI, etc.). Assessment will be performed at screening and then every 8 weeks after the first dose of BI 836845 (Phase I) or after randomization (Phase II) until week 48 and every 12 weeks thereafter. After screening, for each scheduled tumor assessment -7 days and -14 days windows are allowed, respectively before and after week 48. Tumor assessment does not need to be repeated at the screening visit if there are valid results available from assessments which were performed as part of routine clinical practice within 28 days prior to start of treatment. For the phase II part, these need to also meet the requirements in the Imaging Guideline. Patients who discontinue the trial for any reason other than imaging based progressive disease should have a tumour assessment (RECIST 1.1) performed at EOTV before starting new anti cancer therapies (exception to this are patients who have already had tumor assessment within 28 days of EOT visit)

In case of skin lesions, these should be measured with calliper and photographic documentation should be performed. However, skin lesion should not be considered as target lesion in this study.

A bone scan should be performed at screening. If the patient has known bone metastases or if bone metastases are detected at screening, correlative imaging (X-ray or CT scan with bone windows or MRI) of the respective lesion(s) must be done at screening and subsequent imaging time points. Post screening bone scans should also be performed if clinically indicated. Abnormalities suggestive of progression of existing lesions or new lesions must be confirmed by X-ray, CT scan or MRI. Additional tumor assessments performed prior to starting new anticancer therapy/disease progression must also be documented in eCRF.

Proprietary confidential information.

© 2016 Boehringer Ingelheim International GmbH or one or more of its affiliated companies. All rights reserved.

This document may not - in full or in part - be passed on, reproduced, published or otherwise used without prior written permission.

If a patient presented with both irradiated and non-irradiated bone lesions, only the non-irradiated lesions should be followed for tumor assessments unless progression is documented after the radiation.

Follow-up tumor assessments must utilize the same CT/MRI method and acquisition technique as were used for screening assessments to ensure comparability. CT and MRI scan with contrast media should be used except for patients who are allergic/ sensitive to the radiographic contrast media. A chest X-ray or skeletal X-ray which clearly demonstrates a new metastatic lesion may be used to document progression in lieu of CT/MRI/bone scan.

For patients with only bone lesions at baseline, the evaluation of response will be based solely on non-target lesion responses of RECIST 1.1. Specifically, in the absence of new lesions, the overall response at each assessment will be one of the following: Complete Response, Non-CR/Non-PD, Not Evaluable (not assessable, insufficient data) or Progressive Disease. Non-CR/Non-PD would include all assessments not qualifying for Complete Response, Progressive Disease or Not Evaluable. In the presence of any new lesion, the overall lesion response will be Progressive Disease.

In the event of a delay, interruption or discontinuation of treatment, tumor assessment should continue to follow the original schedule. For patients who prematurely discontinue study medication including those discontinued with only clinical disease progression but without radiographic PD, tumor assessments should continue to be performed every 8 or 12 weeks as if the patient remained on study drug until criteria for end of follow-up period are met (refer to [section 6.2.3](#) for details).

